The target population for the study are all school children in 5th-7th grade in primary schools in Asker, Moss and Lillestrøm municipalities in the central-eastern part of Norway. Primary schools with more than 200 students and with a school nurse appointed in at least 50% position are eligible for the study. Eligibility for having a support group established is based on the subjective experience of loneliness by the individual child and is defined as a negative emotional state caused by the discrepancy between the desired and actual social relationships, in line with Peplau et al (1).

Clusters and randomization procedure Since decisions about bullying interventions are typically made at the municipal level, we will begin the recruitment process of schools through enrolment of selected municipalities, as illustrated in figure 2. In selected municipalities consenting to participate, we will randomly invite 26 primary schools from the pool of eligible primary schools in these municipalities.

Figure 2. Illustration of the recruitment process of primary schools in xx, xxx and xxx municipalities in Norway

We will continue enrollment until the pre-identified number of schools is reached. The enrolled schools will be sorted by size and then block-randomized in a 1:1 ratio to either the intervention arm (hereafter referred to as intervention schools) or the control arm (hereafter referred to as control schools). A statistician not involved in the study will carry out the randomization procedure. After randomization, the schools will be informed about their assigned cluster and will receive more detailed information accordingly.

Sample size calculation *School level*: Based on the available literature, we anticipate that 6-10% of children in 5th -7th grade will report bullying (Krusell et al., 2019; Wendelborg, 2021). This proportion is expected to be reduced to at least 6 % in intervention schools' post-intervention. With a significance level at 5% and power at 80%, we will need 721 children in each arm. Accounting for additional variation, we would need 793 in each arm. We assume there will be three classes in each school with about 30 children in each class. Thus, we aim to include 26 schools (13 for each arm) to ensure that the study is sufficiently powered.

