Individual child level: The quality-of-life inventory KIDscreen-27 (28) has 5 domains and is scored from 0-100. For the domain "social support and peers", we anticipate a change of at least 3 points from baseline to 9 months (35). Further, when assuming a correlation of 0.7 to account for statistical dependencies (as the same child is assessed several times), and keeping significance level to 5%, we would need 55 children experiencing loneliness. To account for possible dropouts, we add additional 10% participants, i.e., 60 children.

Study procedure Essential information about the intervention, including the recruitment process and the continuation and follow-up phases will be shared with the municipality, students, parents, teachers and school nurses involved in the project. Written information about the option for support groups for children encountering challenges related to bullying at school will also be provided to parents. **Training Intervention Schools**: A group of two to three teachers or school nurses will participate in a three-day training program centered around the solution-focused approach and the support group model. This training will be led by *Adults for Children*, an organization possessing extensive expertise in implementing interventions within school settings. Following the training, the peer support group intervention will be initiated as soon as possible. **Control Schools**: In the control schools, preventive and health promotion services will be provided as usual and according to the guidelines set forth by the Norwegian Directorate of Health (29).

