Since all children in the study are younger than 16 years of age, consent will be sought from both parents and children who participate in the support group, followed by informed assent by children in all 5ths–7th grade in intervention and control schools. Informed consent will also be sought from parents and children participating in peer support groups (intervention schools). For parents of children in 5-7 classes who do not participate directly in the support group, passive consent will be obtained. In this part of the research, no personally identifiable information will be collected. The questionnaire is anonymous and no name, personal number or other directly identifiable information is asked. No one in the municipality, neither teacher, school nurse, administration staff or others will have access to answers that can be used to identify what individuals have answered. The results will be published through statistics showing how children and young people responded, or how different groups responded (boys or girls). Obtaining consent from all parents for students in the 5th–7th grade is a demanding process that will represent an additional burden and work for the schools. However, every student in 5th–7th grade will be informed of their right to refuse participation or to only assent to certain areas of the survey. They will also be informed that they are free to withdraw from the study at any time. The questionnaire will be conducted in the classroom with a teacher or school nurse present, and there will be minimal risk of being exposed to discomfort, stress, and injury. There will be no direct intervention or interaction. The researchers will conduct thorough research on ethical assessments of risks and develop concrete measures in terms of emergency response.

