
Follow-up of participants

All study support group participants will receive post-study follow-up consultations with the school nurse or social teacher after the intervention. *Adults for Children*'s experience with research involving children and will carefully address the ethical responsibilities, including how to inform children, in their 3-days training program. Participants from *Adults for Children* and the researchers are available for teachers, school nurses, children, and their parents throughout the study. A safety plan is also prepared for additional support should be necessary after the study concludes. If the intervention yields positive effects, all control schools will be invited to implement the intervention as per protocol soon after the conclusion of the study.

Data protection and statistical analysis

We will seek ethical approval for the study from the Regional Ethical Research Committee (REC) in South-East Norway and ensure compliance with data privacy regulations in line with NSD and EUs privacy regulation GDPR. Data will be collected through and stored in the secured server *Tjenester for Sensitive Data* (TSD), integrated solution for collecting and storing sensitive data, managed by the University of Oslo. This includes recording of interview-data through the use of Nettskjema-diktafon in TSD. This is in line with OsloMet's standards for confidentiality and data protection. A risk assessment with appropriate actions will be conducted prior to study implementation.

Baseline data will be presented descriptively. We will use 1600 children (9 schools in each arm) for comparison between intervention- and control schools on school-level. Generalized mixed models (GLM)

for repeated will be used to explore intervention outcomes on individual level for children who were targeted for support groups. GLM will also be used to analyse possible differences on school level. The results will be reported as the estimated between group changes with 95% confidence intervals.

For the process evaluation, descriptive statistical analysis of quantitative data and content analysis of qualitative data will be carried out.

Quality assurance

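### At 9 schools per arm the required 793 children per arm leave only about 2% for non-response; the sample-size section plans 13 schools per arm, and the two must be reconciled

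*Protocol*

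**What the plan says.** Protocol, Sample size calculation, School level. The starting rate is a range, "we anticipate that 6-10% of children in 5th -7th grade will report bullying", and the target is "This proportion is expected to be reduced to at least 6 % in intervention schools' post-intervention". From these, "With a significance level at 5% and power at 80%, we will need 721 children in each arm", and then "Accounting for additional variation, we would need 793 in each arm". On school size, "We assume there will be three classes in each school with about 30 children in each class". The section concludes with a target of 26 schools, 13 per arm.

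Protocol, Data protection and statistical analysis. "We will use 1600 children (9 schools in each arm) for comparison between intervention- and control schools on school-level". The section does not explain the change from 13 to 9 schools per arm, or say whether the 1600 are pupils enrolled or pupils who answer.

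Protocol, Safety Considerations. Pupils in grades 5 to 7 "will be informed of their right to refuse participation or to only assent to certain areas of the survey". No response rate is given for this survey.

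Protocol, Sample size calculation, Individual child level. Here loss is allowed for: "To account for possible dropouts, we add additional 10% participants". The school-level calculation has no corresponding step.

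**The concern.** The school-level survey carries pRQ1 to pRQ3, the only questions that compare the randomised arms. If 9 schools per arm is the working figure, the number to be analysed is almost the whole roll, and the number required is only slightly lower. The only inflation in the calculation is described as covering variation, so it cannot also cover refusals, absences on the survey day and skipped bullying items. Any ordinary loss would then take the randomised comparison below the 80% power on which it was planned. If 13 schools per arm is the working figure, there is ample room, but the analysis section then states the wrong numbers of schools and children. A reader cannot tell which case applies.

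**Working it through.** **Inputs.** Control 10% (the top of the stated range, and the value that reproduces 721), intervention 6%, alpha 5%, power 80%, inflated target 793 per arm, 3 × 30 = about 90 pupils per school. All are from Sample size calculation, School level. The analysis section gives 1600 children and 9 schools per arm. Two-sided testing is inferred because it reproduces the stated figure (one-sided gives 568).

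**Reproducing the plan's figure.** Two proportions, pooled variance under the null, no continuity correction, mean rate 0.08:

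n = [1.960·√(2·0.08·0.92) + 0.842·√(0.10·0.90 + 0.06·0.94)]² / 0.04² = [0.752 + 0.322]² / 0.0016 = 720.9, so 721 per arm.

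721 × 1.10 = 793.1, so 793. Both stated figures reproduce, with an inflation factor of 1.10.

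**Roll and required response.**

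| | 9 schools per arm | 13 schools per arm |
|---|---|---|
| Roll per arm | 9 × 90 = 810 | 13 × 90 = 1170 |
| Roll in total | 1620 | 2340 |
| 1600 as share of roll | 98.8% | 68.4% |
| Response needed for 793 per arm | 793/810 = 97.9% | 793/1170 = 67.8% |

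Since 793/90 = 8.8, nine schools is the smallest whole number that can hold 793 pupils. An arm that lost one of nine schools would have a roll of 720, below even the uninflated 721.

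**Power at lower response.** Let n be the respondents per arm (roll × response), and divide by the protocol's 1.10:

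power = Φ{[0.04·√(n/1.10) − 0.752] / √0.1464}

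Example, 9 schools at 90%: n = 729, n/1.10 = 662.7, so power = Φ[(1.030 − 0.752)/0.383] = Φ(0.726) = 76.6%.

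| Assumed response | 9 per arm: respondents per arm | Power | 13 per arm: respondents per arm | Power |
|---|---|---|---|---|
| 100% | 810 | 80.8% | 1170 | 92.6% |
| 98% | 794 | 80.0% | 1147 | 92.1% |
| 95% | 770 | 78.8% | 1112 | 91.3% |
| 90% | 729 | 76.6% | 1053 | 89.8% |
| 80% | 648 | 71.6% | 936 | 86.1% |
| 70% | 567 | 65.8% | 819 | 81.3% |

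If 1600 children (800 per arm) are in fact analysed, power is 80.3%.

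**Sensitivity to how the inflation is carried.** With 90 pupils per school, a factor of 1.10 corresponds to a school-level intracluster correlation of 0.10/89 = 0.0011. Holding that correlation fixed, rather than the factor, gives 79.0%, 77.0% and 72.4% at 95%, 90% and 80% response with 9 schools per arm. The picture is the same.

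**Sensitivity to class size.** The class size is approximate. With 28 per class the roll of nine schools is 9 × 84 = 756, below 793. With 32 it is 9 × 96 = 864, and the response needed is 793/864 = 92%.

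**The case against.** A reader might infer that the protocol fails to deliver its 80% power. Its own figures do not say that. The stated 1600 children are 800 per arm, more than 793, and give 80.3%. A shortfall appears only when a response rate is brought in from outside, and the document has none. Nor can one say that the respondents must fall below 793 at any realistic response. Safety Considerations describes passive parental consent, an anonymous questionnaire and completion in class with staff present, all of which favour high response. (Quality assurance speaks instead of consent from all parents, which would point the other way.)

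The sample-size section also has slack: 1170 pupils per arm is 47.5% above 793, though the text does not present this as room for non-response. If 13 schools per arm is confirmed, the shortfall disappears down to about 68% response. The required 98% itself rests on an approximate class size. Finally, 1600 may be 2 × 793 = 1586 rounded up, meaning respondents, so it would be a guess to relabel it as the roll.

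All of this stands, and it limits the point to a conditional one. It does not remove it. The analysis section names 9 schools, nothing in the document withdraws that, and at that number there is practically no room for loss. The approximate class size does not supply a dependable margin, because it can move the roll below 793 as easily as above it.

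**Conclusion.** The point holds in conditional form. The analysis section and the sample-size section give different numbers of schools, and the choice decides whether the school-level comparison has room for non-response: about 2% at 9 per arm, about 32% at 13 per arm. At 9 per arm the loss of power is about 1 point at 95% response, 3 points at 90% and 8 points at 80%. At 13 per arm power stays above 80% down to about 68% response.

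The document does not support the stronger conclusion that 80% power is missed outright. That would need both a settled count of 9 schools per arm and a response below about 98%, and the protocol settles neither.

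The figures assume 10% against 6%, two-sided testing, about 90 pupils per school, the response rates shown, and the 1.10 inflation, which the protocol does not explain. If the true clustering is stronger than that factor implies, every power figure here is too high. That is a separate question.

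**What to change.** 1. Reconcile the number of schools between Sample size calculation and Data protection and statistical analysis.
2. State whether 1600 means pupils enrolled or respondents analysed.
3. Define 793 per arm as respondents to the bullying question.
4. State the expected response to that question, with the resulting respondents and power.

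If 9 schools per arm is kept, say that power is below 80% unless about 98% of pupils respond, and give the figure for the expected response: for example, 1458 respondents and 77% at 90%, or 1296 and 72% at 80%. If 13 per arm is kept, correct both the 1600 and the 9 in the analysis section and note that 793 is reached at about 68% response. In either case, say that the power figure depends on the 1.10 inflation.

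The cost is a wording change in two sections. No schools beyond those already planned are asked for. If 9 per arm is kept, the stated power becomes somewhat less favourable.

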Enrolling children in research raises a number of ethical concerns, including consent, confidentiality, and protection from harm (Powell et al., 2016). Children experiencing bullying are particularly vulnerable, underscoring the researchers' responsibility to prevent any additional risks. Conversely, their inclusion can empower children by giving them a voice. Chapter 9a of the Education Act, mandate schools to act if a student is experiencing an unsafe or unfavorable environment. In cases of social exclusion or feelings of loneliness, school nurses, in collaboration with the school staff, are obliged to intervene early at class-, group- or individual level. The support group intervention has the potential to directly benefit participants, aligning with the rights perspective. It can reinforce their sense of being valued individuals who are heard, offering opportunities for significant improvements in their own well-being. These benefits include increased opportunities to acquire knowledge, develop new skills, form new friendships, expand support networks, and have their concerns genuinely acknowledged and addressed. Given their unique perspective, individual children are able to evaluate potential risks to their own well-being. This underscores the importance of effectively communicating with the children, ensuring that they grasp the essence of the intervention and have a clear understanding of what is anticipated from their participation. All study materials will undergo quality assessments by *Adults for Children* to ensure their suitability for the intended age group in terms of language and content. Interpreter services will be made available for families who are not proficient in Norwegian. Children will be clearly informed that they have the right to discontinue the intervention at any point, without any obligation to provide a justification. They will still receive support as normal. Additionally, they will be provided with details regarding whom to contact and how, if they perceive any discomfort. Participants will be encouraged to seek help if an unmet need, such as a mental health concern, is identified. Peers will be supported regularly throughout the study. *Adults for Childrens'* experience with research involving children and will carefully address the ethical responsibilities, including how to inform children, in their 3-days training program.

References

